4.4.1.4 Other Safety Endpoints

4.4.1.4.1 AEs Leading to Study Discontinuation

A flag is available in the clinical database for all AEs in order to identify AEs leading to discontinuation.

In general, the items that are counted are:

- For subject disposition: if subject did not complete the study due to AE as recorded in Completion at End of Study form
- For safety overview: if subject did not complete the study due to AE as recorded in Completion at End of Study form or had any solicited or unsolicited AEs causing study discontinuation / termination as recorded in solicited reaction or unsolicited AE forms within the time period indicated

- For summary of unsolicited AEs by system organ class (SOC) / PT: An unsolicited AE causing study discontinuation as recorded in Unsolicited AE form within the time period indicated

4.4.1.4.2 Solicited Reactions after Any Doses

The rules for calculation are to select the worst case:

- Time period: At least one daily intensity Grade 1, Grade 2 or Grade 3 on the period and considered for at least one injection
- Maximum intensity: Select the maximum overall intensity for any injection
- Time of onset: Select the minimum time of onset for any injection

The worst case cannot be identified for number of days of occurrence and action taken. No tables after any dose will be produced for these endpoints.

4.4.2 Immunogenicity

4.4.2.1 Computed Values for Analysis

For HAI, SN, and ELLA tests, in order to appropriately manage replicate values for analysis purposes, the individual geometric mean (GM) of all values will be computed for each blood sample after managing extreme values as described. The computed value is then considered the titer for that particular blood sample.

- If a titer is < lower limit of quantitation (LLOQ), then the computed value, LLOQ/2, will be used.
- If a titer is \geq LLOQ and < upper limit of quantitation (ULOQ), then the titer itself will be used.
- If a titer is \geq ULOQ (or $>$ ULOQ), then computed value, ULOQ, will be used.

Duplicate records (per subject, antigen, and method) will be recorded for HAI and anti-NA titration. A GM of duplicate will be applied in order to obtain a unique value for the statistical analysis. Unique records will be recorded for SN titration.

Depending on titration method and time, the following computations will be applied:

- If detectable titers (≥ 10 [1/dilution (dil)]) at D0 and 28 days after the last vaccination (D28/D56) for HAI, SN, and anti-NA, the derived ≥ 10 (1/dl) indicator will be “Yes” for that test, otherwise ≥ 10 (1/dil) indicator will be “No”.
- If titer ≥ 40 (1/dil) on D0 and 28 days after the last vaccination (D28/D56) for HAI, the derived ≥ 40 (1/dil) indicator will be “Yes”, otherwise ≥ 40 (1/dil) indicator will be “No”.
- If titer $\geq 20, 40$, and 80 (1/dil) at D0 and 28 days after last vaccination (D28/D56) for SN and anti-NA, the derived $\geq 20, 40$ and 80 (1/dil) indicator will be “Yes” for that test, respectively, otherwise will be “No”.

4.4.2.2 Fold-rise

The derived endpoint fold-rise is driven by both baseline (D0) and post-baseline (D28/D56) computed values as described in [Section 4.4.2.1](#) and is computed as individual titer ratio:

- 28 days after the last vaccination divided by D0 for HAI, SN, and anti-NA.

If the computed fold-increase ≥ 2 for SN and anti-NA, the derived ≥ 2 -fold rises indicator will be “Yes” for that test, otherwise ≥ 2 -fold rises will be “No”.

If the computed fold-increase ≥ 4 for, HAI, SN and anti-NA, the derived ≥ 4 -fold rises indicator will be “Yes” for that test, otherwise ≥ 4 -fold rises will be “No”.

Note: if pre-vaccination (D0) or post-vaccination (D28/D56) values is missing, the fold-rise is missing.

4.4.2.3 Seroconversion

Seroconversion for HAI is defined as a binary indicator. If a pre-vaccination (D0) titer < 10 (1/dil): post-vaccination titer ≥ 40 (1/dil) on 28 days after the last vaccination (D28/D56), or ≥ 4 -fold-rise for subjects with a pre-vaccination titer ≥ 10 (1/dil), the derived seroconversion indicator will be “Yes”, otherwise will be “No”.

Note: if pre-vaccination (D0) or post-vaccination (D28/D56) values is missing, the seroconversion is missing.

4.4.3 Efficacy

For each subject, the efficacy endpoints will be derived based on a combination of the following items:

ILI occurrence: at each ILI visit, the occurrence of a temperature of $\geq 100.4^{\circ}\text{F}$ (38°C), starting more than 14 days after the 1st vaccination for the Full Analysis Set for Efficacy (FASE) as defined in [Section 5.2.1](#) and last vaccination for the Per-Protocol Analysis Set for Efficacy (PPASE) as defined in [Section 5.2.2](#) and concurrent with at least one other symptom meeting the definition of an ILI¹ will be considered as an ILI occurrence.

Notes:

- The start date of the ILI is the start of fever $\geq 100.4^{\circ}\text{F}$ (38°C)
- Start and end dates of fever are considered as the start and end date of the ILI (when the end date is unknown, the last date the fever is known to be present is used)
- The date of start / end of each symptom is used in comparison of start and end of fever $\geq 100.4^{\circ}\text{F}$ (38°C) to define concurrent symptoms with ILI: when start and end dates for fever and one other protocol-defined symptom are not missing, the start date for fever is \leq the end date for the symptom and the end date for fever is \geq the start date for the symptom

¹ Cough, wheezing, difficulty breathing, nasal congestion, rhinorrhea, pharyngitis (sore throat), otitis, vomiting, diarrhea, shivering, fatigue, headache or myalgia

- After the end of an ILI episode, an interval of 2 days has to pass before a new ILI episode can be considered
- For the primary and secondary objectives, in case of more than one occurrence of the same efficacy endpoint for the same subject, only the first occurrence based on the start date of the fever ($\geq 100.4^{\circ}\text{F}$ [38°C]) is considered for the estimation of vaccine efficacy for the prevention of this endpoint

Modified CDC-defined ILI is the occurrence of a temperature of $\geq 100.4^{\circ}\text{F}$ (38°C), starting more than 14 days after the first vaccination and concurrent with cough or pharyngitis (sore throat). The same derivation rules for ILI occurrence will be used.

PCR-confirmed influenza case: An ILI occurrence is PCR-confirmed as positive for influenza A or B types if the PCR result of the corresponding NP swab, recorded at the corresponding ILI visit in the database and taken within 10 days after the start of the ILI, is positive for influenza.

Culture-confirmed influenza case: An ILI occurrence is culture-confirmed as positive for influenza A or B types if the virology result of the corresponding NP swab, recorded at the corresponding ILI visit in the database and taken within 10 days after the start of the ILI, is positive for influenza.

Laboratory-confirmed influenza case: An ILI occurrence is laboratory-confirmed as positive for influenza A or B types if it is either PCR- or culture-confirmed (see above).

Strain: Virus strains used for sequencing and vaccine formulations for similarity assessment will be detailed in a separate Appendix to this Statistical Analysis Plan (SAP) when it is available and can be updated up to the database lock.

Genetic similarity: Genetic similarity is defined when a laboratory-confirmed isolate is deemed similar to one of the viral strains contained in the vaccine formulations according to sequencing of full HA gene segments proteins. A strain is considered similar to one of the vaccine strains included in the formulation of the considered season if the sequence of full HA gene matches $\geq 99\%$ with a strain known to be and pre-defined as vaccine-similar. This will be defined in a separate Appendix to this SAP when it is available and can be updated up to the database lock.

Antigenic similarity: Antigenic similarity is defined when a laboratory-confirmed isolate is deemed similar to one of the viral strains contained in the vaccine formulations according to Ferret Antigenicity testing (HAI against a panel of known standard ferret reference antisera).

Similarity to vaccine components: For prevention of laboratory-confirmed influenza illness caused by viral strains similar to those contained in the vaccine in subjects 6 months through 35 months of age, laboratory-confirmed isolate is deemed similar to one of the vaccine components based on antigenic similarity only. For all the other endpoints, similarity is based on antigenic similarity when available or based on genetic similarity otherwise.

Potentially, the same swab can be linked to several ILIs, and several swabs may be taken for the same ILI. Therefore, occurrences of positive swabs attached to an ILI are not necessarily equal to occurrences of ILIs with positive swab.

4.4.4 Derived Other Variables

4.4.4.1 Age for Demographics

The age of a subject in the study will be the calendar age in months at the time of inclusion.

For randomization stratification and subgroup analyses, the 2 following classes of age will be used: < 24 months and \geq 24 months.

4.4.4.2 Breastfeeding

For subjects who have been breastfed, the duration of breastfeeding in weeks will be derived as:

$$(\text{end date} - \text{start date} + 1) / 7$$

If the end date is missing and the breastfeeding is ongoing at inclusion, the duration of breastfeeding in weeks will be derived as:

$$(\text{first vaccination date} - \text{start date} + 1) / 7$$

Missing or partially missing dates will not be imputed except for the missing day where for start date the missing day is replaced with the first day of the month and for end date the missing day is replaced with the last day of the month to derive the duration of breastfeeding.

4.4.4.3 Vaccine Formulation

The vaccine formulation will be derived as:

- Formulation = “Formulation 0” for all subjects in the Sentinel Safety Cohort
- Formulation = “Formulation 1” for all subjects included in Season 1
- Formulation = “Formulation 2” for all subjects included in Season 2
- Formulation = “Formulation 3” for all subjects included in Season 3

If the same formulation is used in 2 or more seasons, analyses per formulation will be performed by pooling seasons using the same formulations.

4.4.4.4 Occurrence of symptoms / events associated with ILI

For observational objectives, symptoms / events are considered to be associated with any ILI or laboratory-confirmed ILI including AOM, ALRI, medication use, hospitalization (recorded as Inpatient Hospitalization in Health Care Utilization form), emergency room visits (recorded as Outpatient Hospitalization in Health Care Utilization form), non-routine medical office visits (recorded as Outpatient Visit in Health Care Utilization form), absenteeism due to child sick days if the start date of the event is within 30 days after the start of the ILI ($0 \leq \text{start date of symptom / event} - \text{start date of fever} \leq 30$ days).

Duration of ILI symptoms is defined as end date – start date + 1.

4.4.4.5 Medical history of interest

Medical history of interest are those pre-listed in Chronic Medical History form: asthma, chronic lung disease, pulmonary hypertension, cystic fibrosis, congenital heart disease, cystic kidney disease, renal insufficiency, sickle cell trait, thalassemia major and minor, febrile seizure, egg allergy, eczema, and diabetes mellitus.

An indicator of baseline medical history of interest will be derived as “Yes” if a subject has at least one of the pre-defined medical history and “No” otherwise.

5 Statistical Methods and Determination of Sample Size

The statistical analyses will be performed under the responsibility of the Sponsor’s Biostatistics platform using SAS® Version 9.4 software or later. Graphics may be produced using R.

The results of the statistical analysis will be available in the final clinical study report (CSR).

For descriptive purposes, the following statistics will be presented:

Table 5.1: Descriptive statistics produced

Baseline characteristics and follow-up description	Categorical data	Number of subjects. Percentage of subjects.
	Continuous data	Mean, standard deviation (SD), quartiles (first quartile [Q1], median, third quartile [Q3]), minimum, and maximum.
Clinical safety results	Categorical data	Solicited: Number and percentage (95% confidence intervals [CIs]) of subjects. Unsolicited: Number and percentage (95% CIs) of subjects, and number of events.
Immunogenicity results	Categorical data (eg, seroconversion, cutoff, 4-fold-rise)	Number and percentage (95% CIs) of subjects.
	Continuous data (titer)	Log10: Mean and standard deviation. Anti-Log10 (work on Log10 distribution, and anti-Log10 applied): Geometric mean, 95% CI of the geometric mean, quartiles, minimum, and maximum. Graphical representation by Reverse Cumulative Distribution Curve (RCDC).
Efficacy results	Categorical data	Number and percentage (95% CIs) of subjects. Number of cases, relative vaccine efficacy (rVE) and 95% CIs

The CI for the single proportion will be calculated using the exact binomial method (Clopper-Pearson method, quoted by Newcombe (12), ie, using the inverse of the beta integral with SAS®).

For immunogenicity results, assuming that Log10 transformation of the titers follows a normal distribution, at first, the mean and the 95% CI will be calculated on Log10 (titers) using the usual calculation for normal distribution (using Student's t distribution with n-1 degree of freedom), then antilog transformations will be applied to the results of calculations, in order to provide GMs and their 95% CI.

Rounding rules on descriptive statistics will follow the Sanofi Pasteur standard. To present percentages (and 95% CI of percentages), one digit after the decimal place will be used by default (ie, for a large number of outputs). However, 2 digits may be used for some numbers, such as percentages of influenza cases (typically for relative vaccine efficacy [rVE]).

5.1 Statistical Methods

5.1.1 Hypotheses and Statistical Methods for Primary Objective

5.1.1.1 Hypotheses

Non-inferiority efficacy hypotheses:

$$H_0: rVE \leq -10\%$$

$$H_A: rVE > -10\%$$

Superior efficacy hypotheses:

$$H_0: rVE \leq 5\%$$

$$H_A: rVE > 5\%$$

5.1.1.2 Statistical Methods

Efficacy

The rVE of QIV-HD relative to QIV-SD will be compared in a step-wise manner:

A non-inferiority testing approach will be applied first, using a non-inferiority margin of -10%. If non-inferiority is demonstrated, a superiority test will be applied using a superiority margin of 5%. Both tests will use a one-sided Type I error at 2.5% if the interim analysis at the end of Season 2 is not performed, and there is no need for multiplicity adjustment due to the step-wise approach.

The rVE of QIV-HD to QIV-SD will be estimated for primary endpoint as follows:

$$rVE = (1 - (C_{HD} / N_{HD}) / (C_{SD} / N_{SD})) \times 100\%$$

where:

- C_{HD} and C_{SD} are the numbers of influenza cases meeting the considered primary endpoint definition in the QIV-HD and QIV-SD groups, respectively.
- For analysis in PPASE, the first episode among those occurring more than 14 days after the last vaccination will be considered. For analysis in FASE, the first episode among those occurring more than 14 days after the first vaccination will be considered.
- If subject experiences multiple occurrences of the same endpoint, only the first episode will be considered
- N_{HD} and N_{SD} are the numbers of subjects in the QIV-HD and QIV-SD groups, respectively.

CIs for rVE will be calculated by an exact method assuming a binomial distribution of the number of cases in the QIV-HD group conditional on the total number of cases in both groups.

The rVE of QIV-HD will be considered as non-inferior to QIV-SD if the lower bound of the rVE is $> -10\%$, and superior to QIV-SD if the lower bound of the CI for the rVE is $> 5\%$. The PPASE will be used as the primary analysis set for the non-inferiority test and the FASE will be used as the primary analysis set for the superiority test.

If the interim analysis is conducted, an alpha spending method quoted by Lan and Demets (power family, $\phi=2$) will be used to maintain an overall Type I error (the 'alpha') of 0.025 one-sided, considering that [REDACTED] of information time is reached at the time. Consequently, a one-sided nominal alpha of [REDACTED] will be used at interim and final analysis, respectively. This corresponds to [REDACTED] two-sided CIs to be used at interim and final analysis, respectively. If the interim analysis is not conducted or if the superior rVE is concluded at the interim analysis with the most stringent [REDACTED] threshold (ie, the stopping rule for superior efficacy is fulfilled), the final analysis will be performed with one-sided alpha of 0.025 without multiplicity adjustment.

A complementary analysis of comparing Kaplan-Meier curves between QIV-HD and QIV-SD groups for the primary endpoint will be performed for all subjects and stratified by age group and previous vaccination history:

- Start date: D0 (first vaccination date)
- Event date for subjects with a protocol-defined ILI is the start date of the first fever episode
- End date for subjects without a protocol-defined ILI is the last visit or contact date whichever is later

The non-inferiority test on the FASE and the superiority test on the PPASE will be performed as sensitivity analyses.

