9.2 Primary Endpoints and Assessment Methods

9.2.1 Efficacy

9.2.1.1 Efficacy Endpoints

The primary endpoint for the evaluation of efficacy is the occurrence of laboratory-confirmed influenza illness (≥ 14 days post-vaccination) caused by any influenza viral types/subtypes, in association with a protocol-defined ILI.

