5.1.2.2 Statistical Methods

Efficacy

If the primary objective is demonstrated, the secondary confirmatory objectives will be tested. A hierarchical testing combined with a graphical approach will be used to adjust the multiplicity of the 3 secondary confirmatory efficacy objectives, which prevents any inflation of the overall one-sided Type I error beyond 2.5%.

For the 1st secondary objective, a superiority test using a more stringent margin of [REDACTED]

[REDACTED] will be performed only after the primary objective is demonstrated. No multiplicity adjustment is needed, and the same nominal alpha levels for the primary objective being used in the interim analysis (ie, one-sided [REDACTED]) and in the final analysis (ie, one-sided [REDACTED] if the stopping rule for superior efficacy is not fulfilled at the interim analysis or one-sided 0.025 without adjustment if otherwise) will be used. The FASE will be used as the main analysis set and the same analysis on the PPASE will be performed as a sensitivity analysis.

Additional sensitivity analyses for the primary and 1st secondary objectives will be performed as follows using the same statistical method for the final analysis of the primary endpoint as detailed above:

- Excluding all siblings participating in the study to evaluate potential bias due to within-siblings flu contamination. For this, any subjects who had a sibling enrolled in this study will be excluded
- Considering the first ILI episode as defined in [Section 4.4.3](#) but occurring from the first dose for the primary endpoint on the PPASE and FASE respectively

At the time of the final analysis, if superiority for the 1st secondary objective is demonstrated, a graphical approach of Holm with full alpha-propagation will be applied to control alpha within the 2nd and 3rd secondary efficacy objectives. If one of the 2nd and 3rd objectives is claimed for efficacy using a two-sided 97.5% CI, then the other one will be tested using a two-sided 95% CI to assess superiority. QIV-HD will be considered as superior to QIV-SD if the lower bound of the CI for the corresponding rVE is > 0%. Estimation of rVE for these two secondary efficacy objectives will be the same as those described for the primary objective above in [Section 5.1.1.2](#). The FASE will be used as the main analysis set and the same analysis on the PPASE will be performed as a sensitivity analysis.

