The likelihood of achieving the expected [REDACTED] per-protocol lab-confirmed influenza cases for the primary endpoint at the end of the Season 3 will be assessed using the weekly number of reported ILI in the CRB (laboratory positivity for influenza need not have been confirmed yet) available in Season 3. It is assumed that after the peak number in the same season occurs the weekly number of reported ILI is exponentially distributed in a monotonically decreasing manner. An exponential regression curve will be plotted to forecast the weekly number of reported ILI until the end of the surveillance period in Season 3. Then, the predicted number of per-protocol cases for the primary endpoint at the end of Season 3 will be calculated as follows:

- 1) Calculate the total number of future ILI until the end of Season 3 based on weekly number of future ILI as forecast above
- 2) Multiply the positivity factor estimated from Season 1 to obtain the total number of future cases for the primary endpoint where the positivity factor is the number of cases for the primary endpoint divided by the number of ILI (Note: Season 2 data may be considered for a more conservative prediction)
- 3) Multiply the per-protocol factor estimated from the observed cases (ie, the number of per-protocol cases divided by the total number of cases for the primary endpoint)
- 4) Add the number of per-protocol cases already observed in the study

If laboratory results are available during this analysis, then observed cases for the primary endpoint in Season 3 will be used directly for the prediction using exponential regression.

Epidemiological data of influenza occurrence may be taken into count for the prediction of weekly number of reported influenza cases for the remaining season.

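### Supportive time-to-event analyses: the Kaplan-Meier rules refer to any ILI rather than laboratory-confirmed influenza, the Cox trigger does not measure drop-out imbalance, and the Cox fallback keeps one constant vaccine hazard ratio

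*SAP*

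**What the plan says.** **Kaplan-Meier curves.** SAP 5.1.1.2 states: "A complementary analysis of comparing Kaplan-Meier curves between QIV-HD and QIV-SD groups for the primary endpoint will be performed for all subjects". Time starts at first vaccination. Two rules follow: "Event date for subjects with a protocol-defined ILI is the start date of the first fever episode" and "End date for subjects without a protocol-defined ILI is the last visit or contact date whichever is later". Protocol 9.2.1.1 defines the primary endpoint as "occurrence of laboratory-confirmed influenza illness (≥ 14 days post-vaccination) caused by any influenza viral types/subtypes", in association with a protocol-defined ILI.

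**Cox model.** Protocol 12.3.1 plans, without condition, a time-to-event analysis for the primary objective to address unequal drop-out between groups, and leaves further details to the SAP. SAP 5.3.1 makes that analysis, a Cox model comparing the two vaccine groups, conditional on the attrition rate for the PPASE being above 10%.

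**Fallback.** If Schoenfeld residuals indicate that proportional hazards is violated, SAP 5.3.1 calls for a Cox model stratified by season and age group.

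**The concern.** (a) An ILI is not a case. SAP 4.4.3 adds a separate step: "An ILI occurrence is laboratory-confirmed as positive for influenza A or B types if it is either PCR- or culture-confirmed". SAP 5.4.3 predicts cases from ILI counts by a ratio: "the positivity factor is the number of cases for the primary endpoint divided by the number of ILI". A programmer who follows the Kaplan-Meier bullets to the letter would therefore plot first ILI of any cause, a different endpoint on which any vaccine difference is diluted. The end-date rule also lets follow-up run past the date when swabs stop and a case can no longer be confirmed.

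(b) The stated purpose is imbalance between groups, but no between-group difference enters the trigger. Nor is the measured quantity defined. It could be drop-out, or loss from FASE to PPASE, which under SAP 5.2.2 includes second-dose timing and other deviations.

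(c) Stratification lets baseline hazards differ between seasons and age groups. It does not let the vaccine effect vary with time, which is the assumption at stake in a model that compares only the two vaccine groups.

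**Working it through.** No figure of the plan can be reproduced, because attack rate, true rVE, case numbers and power are redacted. The rates below are assumptions.

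**(a) Literal reading of the Kaplan-Meier bullets.** Assume constant hazards over 180 days, no vaccine effect on influenza-negative ILI, an SD attack rate of 6%, influenza as 20% of ILI, and a true rVE of 25% on the hazard scale.

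- Influenza hazard, SD: −ln(1 − 0.06) = 0.0619. HD: 0.75 × 0.0619 = 0.0464.
- Influenza-negative ILI hazard, both groups: 0.0619 × 0.8/0.2 = 0.2475.
- First ILI of any cause, SD: 1 − exp(−0.3094) = 26.6%. HD: 1 − exp(−0.2939) = 25.5%.
- Contrast in cumulative incidence: 1 − 0.2547/0.2661 = 4.3%. On the hazard scale: 1 − 0.2939/0.3094 = 5.0%.
- Same contrast with confirmed influenza as the event: 1 − 4.53%/6.00% = 24.4%.

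With influenza at 10–30% of ILI, an attack rate of 4–8% and rVE of 20–30%, the literal reading shows 1.3–8.5% (hazard scale 2.0–9.0%).

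**End of follow-up.** Protocol Tables of Study Procedures 3 and 4 place the last call at D180 (one dose) or D208 (two doses), or at season end if later. Swabs stop on 30 April (NH) or 31 October (SH). Counting back from those dates, the call falls after swabbing ends for these children:

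| Season (Protocol dates) | One dose, first vaccinated after | Two doses, first vaccinated after |
|---|---|---|
| Season 1 NH, ends 30 April 2023 | 1 November 2022 | 4 October 2022 |
| Season 2 SH, ends 31 October 2023 | 4 May 2023 | 6 April 2023 |

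They stay in the risk set with no chance of a confirmed event. Because this applies to both groups alike, it lowers both curves and should change the contrast little.

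**(b) Trigger.** With 1:1 allocation the overall drop-out rate is the mean of the two group rates. The effect on the count-based estimate assumes a true rVE of 0 and half a season lost per drop-out: rVE = 1 − (1 − 0.5·d_HD)/(1 − 0.5·d_SD).

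| HD / SD drop-out | Overall | Cox model fitted? | Count-based rVE |
|---|---|---|---|
| 14% / 4% | 9.0% | no | 1 − 0.93/0.98 = 5.1% |
| 11% / 8% | 9.5% | no | 1 − 0.945/0.96 = 1.6% |
| 10.5% / 10.5% | 10.5% | yes | 0% |

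If attrition means all loss from FASE to PPASE, other exclusions above 1.0 or 0.5 percentage points would trigger the model in the first two rows on the same drop-out.

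**(c) Fallback.** Simulations of 400 trials per scenario used 12,000 children, six season-by-age strata with different baseline hazards, 180 days of follow-up, and a vaccine hazard ratio that changes at day 90.

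| True HR to day 90 / after | Unstratified HR | Stratified HR | Proportional hazards rejected |
|---|---|---|---|
| 0.55 / 1.00 (mean 647 cases) | 0.773 | 0.773 | 88% with either model |
| 0.65 / 0.85 | 0.747 | 0.747 | 29% and 30% |

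Both models return roughly the midpoint, (0.55 + 1.00)/2 = 0.775 and (0.65 + 0.85)/2 = 0.75. Stratifying changes neither the estimate nor, materially, the test. Period-specific fits recover 0.55 and 1.00, and 0.65 and 0.85.

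**The case against.** On (a), the heading of the Kaplan-Meier paragraph names the primary endpoint, and SAP 5.1.2.2 uses similar shorthand for that endpoint ("Considering the first ILI episode as defined in" SAP 4.4.3). SAP 4.4.3 counts the first occurrence of the same endpoint by fever onset, and the rVE rules in SAP 5.1.1.2 take the first episode among those meeting the endpoint. Laboratory-confirmed cases were therefore probably meant, and the dating can be recovered. This stands, and it confines the dilution to the literal reading.

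It also disposes of two stronger inferences a reader might draw. One is that children with only influenza-negative ILI have no end date. That requires one bullet to be read as shorthand and the other literally; read consistently, such a child is either an event or is censored. Even leaving these children out would move the central contrast only from 24.4% to 24.1%. The other is that confirmed cases preceded by a negative ILI would be dated too early. That holds only if the first-occurrence rules are set aside.

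On (b), the trigger sits in the missing-data section and its sentence speaks of drop-out, so drop-out is the natural meaning. The Kaplan-Meier comparison, the drop-out plots by group and reason (SAP 5.3) and the tipping-point analysis (SAP 5.3.1) all run without condition. Drop-out imbalance is thus examined; what can be missing is the Cox estimate.

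On (c), an averaged hazard ratio is not an error, and stratification is a valid remedy for differing baseline hazards. The curves and the 14–90-day observational endpoint (Protocol 9.4.1.1) give some view of change over time. Still, neither supplies the estimate that a failed proportionality check on the vaccine effect calls for.

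**Conclusion.** The point holds for supportive analyses only and is minor to moderate. The wording defects can be read directly from the documents; the sizes rest on assumed rates.

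- (a) Followed literally, the bullets plot the wrong endpoint and shrink a contrast of about 25% to about 4%. Under the probable intent the contrast hardly changes, and follow-up beyond surveillance matters little.
- (b) The trigger can suppress the Cox estimate when drop-out is imbalanced and produce it when drop-out is equal, although the protocol states the analysis without condition.
- (c) The fallback leaves a time-varying vaccine effect unaddressed.

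A reader might infer that the primary conclusion or its Type I error is at risk. The documents do not support that: the confirmatory decision uses the exact conditional binomial interval, which depends on none of these rules.

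**What to change.** **SAP 5.1.1.2.** Define the event as the first laboratory-confirmed primary-endpoint case in the set-specific 14-day window (after first vaccination for the FASE, after last vaccination for the PPASE), dated at that episode's fever onset. Censor all others, including children with only influenza-negative ILI, at the earlier of last contact and end of surveillance (30 April NH, 31 October SH).

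**SAP 5.3.1, trigger.** Remove the 10% condition so that the Cox analysis is always reported beside the planned Kaplan-Meier comparison.

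**SAP 5.3.1, fallback.** Keep the stratification by season and age group. If proportional hazards fails for the vaccine effect, also report period-specific hazard ratios or cumulative-incidence ratios, with the periods fixed in advance.

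The cost is SAP wording and programming. The dates and laboratory results needed are already collected, and no confirmatory test, alpha level or sample size changes.
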